Bipolar disorder (BD) is a severe and debilitating psychiatric illness. While available treatments benefit about 50%-60% of patients, there is a sizeable group that does not respond adequately. Bipolar depression often presents a very significant challenge for clinical management as treatment responses are often inadequate. The pathophysiology of depression is not agreed on but there is evidence for contributions of neuroinflammation and disturbed brain arachidonic acid metabolism. Furthermore, an increasing body of evidence documents a role for increased oxidative stress in brain neurons as a putative mechanism involved in neuronal damage and possibly in the pathophysiology of mood disorders. Lithium and valproate, the most commonly used medications to treat BD, have been shown in pre-clinical studies to have important effects on neuroinflammatory mechanisms, as well as oxidative stress pathways. The non-steroidal anti-inflammatory drug (NSAID) Celecoxib, a cyclooxygenase type 2 (COX-2) inhibitor, was shown to have possible effects in bipolar depression in a small double-blind controlled preliminary study. A controlled study testing the potential of aspirin in symptomatic schizophrenic patients found promising results. A double-blind placebo-controlled study also suggested therapeutic effects of N-Acetyl Cysteine (NAC) for depressive symptoms in patients with bipolar disorder. Therefore, there is a compelling rationale for conducting a double-blind controlled trial to **examine the potential of aspirin and NAC in the treatment of BD patients**. We propose to conduct a 16-week double-blind randomized placebo controlled trial with aspirin (1000 mg qam, orally) or NAC (1000 mg bid, orally) as add-on treatments to mood stabilizing agents in BD type I and II patients on a depressive or mixed episode. In addition to testing these treatments individually, we will also randomly assign patients to a combination of aspirin and NAC, to examine the potential for synergistic effects from these two medications. We will utilize a **novel drop-the-loser (DTL) adaptive clinical trial design** that is more cost-effective to screen medication leads. . This study will investigate the role of inflammatory mechanisms and oxidative stress in antidepressant response and could lead to the development of new and critically needed treatment modalities for BD patients.

## **Introduction and Background**

Bipolar disorder (BD) is a major health problem (lifetime prevalence about 1.5%) and causes significant morbidity and burden to society. Available treatments help a substantial proportion of patients but are not beneficial for an estimated 40%-50% [1, 2]. Lithium has been the standard treatment for BD over many years [3, 4], but may have significant side effects and not be efficacious in 50-60%. Over the past two decades, several alternatives have been developed [1, 5-9] [10, 11][12-19]. Nonetheless, there still is considerable need for better treatments and understanding of disease and drug mechanisms involved [20, 21], as disability and functional impairment are still widespread amongst individuals suffering from BD.

Although the exact pathophysiology of BD and particularly of bipolar depression is unknown, evidence suggests important contributions of neuroinflammation associated with upregulated brain arachidonic acid (AA) metabolism [22, 23]. Clinical studies support the idea that BD and depression involve a brain inflammatory response and disturbed AA metabolism [24-27]. Increased levels of PGE2 are present in platelets, saliva, and CSF of depressed patients [28-32]. In addition, increased blood levels of proinflammatory markers, particularly C-reactive protein, soluble interleukin (IL)-2 receptor, IL-6 and tumor necrosis factor (TNF)-alpha, have been reported in BD mania [33], as have increased blood levels of markers of oxidative stress (superoxide dismutase activity and catalase activity, serum thiobarbituric acid reactive substances (TBARS)) [34] [35].

*In vivo* rodent [36-40] and human studies [41] suggest that the inhibition of AA metabolism and the COX-2 pathway may be a common mechanism of action of mood-stabilizing drugs [22, 23]. With previous support from the Stanley Medical Research Institute (PI: [name]), we completed a first double-blind controlled trial with celecoxib, a selective inhibitor of COX-2, as adjunctive treatment for bipolar depression and found a non-significant but potentially clinically meaningful effect for an early, but not sustained therapeutic response [42]. Together, these preclinical and clinical findings provide strong evidence that increased COX-2 mediated PG production is involved in the pathophysiology of mood disorders, and thus that inhibition of inflammatory mechanisms is a possible avenue for antidepressant response and mood stabilization.

Another NSAID known to target AA metabolism is aspirin, which is commonly used to treat peripheral inflammation and fever. Aspirin's effects are believed to be due to decreased production of pro-inflammatory prostaglandins (PGs) and thromboxanes (TXBs), due to inhibition of COX enzymes [43]. However, an additional antiinflammatory mechanism recently was proposed. Aspirin can acetylate COX-2, and the acetylated enzyme can convert DHA to 17-OH-DHA, an antiinflammatory agent that is a precursor of anti-inflammatory resolvins [44]. In this regard, aspirin may have a synergistic interaction with lithium, which was shown to increase the brain concentration of 17-OH-DHA and reduce brain concentrations of proinflammatory PGE2 and TXB2 in a rat neuroinflammation model [45].

Preliminary clinical studies suggest a therapeutic effect of aspirin in mood disorders. One study reported that aspirin ameliorated mood in males undergoing coronary angiography [46]. A retrospective clinical pharmacoepidemiological study reported that chronic aspirin reduced the incidence of clinical worsening in patients taking lithium [47]. Additionally, a randomized double blind placebo-controlled trial reported that adjuvant aspirin therapy (1000 mg/day, 12-weeks) reduced symptoms of schizophrenia spectrum disorders, in which neuroinflammation likely plays a role [48, 49].

Increased oxidative stress may be involved in pathophysiology of mood disorders [50]. Glutathione is a key substrate for antioxidant functions in cells. Its production is limited by its precursor, cysteine. N-Acetyl Cysteine (NAC) is the acetylated derivative of cysteine. It is more bioavailable. NAC has been shown to be neuroprotective [51]. If abnormalities in oxidative stress are key mechanisms involved in pathophysiology of mood disorders, it is compelling to hypothesize that effective antioxidant drugs will have effects in alleviating the symptoms or changing the course of the illness. Lithium and valproate have been shown to have important effects on glutathione-mediated processes [52]. In a clinical trial, lithium was shown to have effects on markers of oxidative stress in patients with bipolar disorder in the manic state [53]. Berk et al [54] reported a 24 wk double-blind placebo controlled trial with NAC

as adjunct to ongoing mood stabilizing medications in patients suffering from BD where there were significant effects on depressive symptoms. Recently, results of an open label study also revealed positive results on bipolar depression during a two month extension period [55]. Furthermore, these same authors demonstrated effects of NAC on certain symptomatic domains in patients with schizophrenia, primarily on negative symptoms [56].

**In view of these compelling preclinical and clinical observations, a study to test whether aspirin and NAC will ameliorate BD symptoms is highly warranted.** Our study will include measurements of cytokines, inflammatory factors and markers of oxidative stress **at baseline, at 8 wks and at 16 wks** to test the hypothesis that these are mediators or modulators of therapeutic response. Our proposed study will investigate the role of neuroinflammation and oxidative stress in antidepressant response in BD and could lead to the development of new therapeutic agents for patients that may enhance or replace failed responses to commonly used medications.

### **Specific Aims**

We propose to conduct a double-blind placebo-controlled trial with a widely available and prototypical non-steroidal anti-inflammatory agent, aspirin, and an antioxidant agent, NAC, involving symptomatic BD type I and II patients having a depressive or mixed episode. This will be the first controlled study to test the hypothesis that aspirin and NAC, by themselves or in combination, will be beneficial in treating depression in bipolar disorder patients and in promoting mood stabilization. We propose to utilize a novel drop-the-loser (DTL) adaptive design that will be more cost-effective in screening new medication leads.

Our study has the following Aims: Aim I – Examine efficacy of aspirin in treating depression in bipolar patients in a double-blind placebo-controlled add-on design; Aim II – Examine efficacy of NAC in treating depression in bipolar patients in a double-blind placebo-controlled add-on design; Aim III – Examine efficacy of combined treatment with aspirin and NAC looking for synergistic, potentiating effects; Aim IV – Examine the role of markers of neuroinflammation, oxidative stress and cytokines as possible mediators or modulators in therapeutic response in the treatment of depression in patients with BD.

### **Need for efficient drug development studies**

Most conventional, medication-development trials in psychiatry have employed standard, fixed, parallel-group designs, involving only a few drug conditions and very large sample sizes. Trials designed in this manner have been criticized for being exceedingly long, expensive, and often uninformative if initial drug or dose selection proved to be incorrect. Two ways in which the clinical trial enterprise may be enhanced are the implementation of adaptive clinical trial designs and the application of Bayesian statistical approaches in monitoring and analyzing clinical trials [57, 58].

Adaptive designs permit critical mid-trial design modifications, based on interim analyses, without undermining the validity and integrity of the trial [59]. Adaptations to the trial are pre-specified (by design); not made in an unplanned or ad hoc manner. These adaptations are aimed at providing (1) better treatment of patients by limiting exposure to non-effective drugs or drug combinations and increasing exposure to more effective drugs or drug combinations; (2) more efficient drug development; and (3) better use of available resources.

A drop-the-loser (DTL) adaptive design is useful in phase II clinical development especially when there are uncertainties regarding the most promising drug to which Phase III resources should ultimately be allocated [60, 61]. DTL designs permit multiple treatment arms allowing for the rapid assessment of candidate drugs or drug combinations. An interim analysis plan specifies the criteria for dropping doses that fail to show clinically meaningful efficacy over placebo. Conditions satisfying interim efficacy criteria are continued to completion. This adaptive pruning permits the randomization of remaining participants to the drug condition(s) which demonstrate the most promise. As a consequence, adaptive DTL designs permit initial evaluation of a broader range of drugs or drug combinations followed by increasing the precision of effect size estimates for the more promising treatment(s).

The recommended analysis strategy when using adaptive trials is Bayesian [57] which permits statements about the probability that treatment confers benefit. This probability is calculated by combining existing information,

represented by a prior distribution, with observed data, represented by the likelihood. This yields a posterior distribution from which statements about the probability of a given effect size can be made. As treatment outcomes accumulate over the course of the trial, posterior probabilities are used to estimate treatment effects and inform the pruning of less effective treatments based on a priori decision rules.

Designing an adaptive trial typically begins with a simulation study to address issues such as timing and frequency of interim analyses, and to understand the operating characteristics associated with the criteria for dropping conditions [57]. In keeping with the proposed DTL design, a Monte Carlo simulation study was conducted (see Statistical Analyses) to assess the relative merits of this design over a non-adaptive parallel-group approach. Simulation results, support the proposed DTL design in showing that under scenarios reflecting the hypothesized treatment effects, the adaptive design allocates more subjects to the more promising treatment conditions, i.e., appropriate “pruning” of less effective conditions. Using simulated data, the design performs well as demonstrated by adequate power and Type I error rates. Thus, employing the proposed DTL design is likely to yield the same conclusions as the classical fixed (non-adaptive) design, but with greater statistical precision for the most promising treatments.

### **Study Design**

BD type I or II patients (n=160), on a depressive or mixed episode, who were on therapeutic doses of any of the commonly utilized mood stabilizing agents (lithium, anticonvulsants, atypical antipsychotics) for at least one month and who were still symptomatic (MADRAS >20) will be enrolled. Patients will be randomly assigned to orally receive one of 4 conditions: aspirin 1000 mg (2 capsules of 500 mg) qam, NAC 1000 mg (2 capsules of 500 mg) bid, combined aspirin and NAC at same doses as given individually or matched placebo, as an add-on medication to their ongoing treatment regimen, for an 16-week double-blind trial. After the first 8 week of the double blind treatment, the responders will keep taking the same study drug, whichever it is. And the non-responders will be re-randomized for one of the other three groups of study drugs they haven't tried yet.

### **Patient sample:**

#### Inclusion criteria:

- 1) Age 18 to 65 years
- 2) A diagnosis of BD type I or II according to SCID-I interview;
- 3) Currently in a depressive or mixed episode, based on DSM-IV/ SCID-I criteria;
- 4) MADRAS >20 at entry in the study;
- 5) No CURRENT liver, kidney, heart disease or ulcers or bleeding dyscrasia;
- 6) No HYSTORY of kidney dysfunction or cardiac problems;
- 7) ON therapeutic doses of a mood stabilizing drug (lithium, anticonvulsants, any atypical antipsychotics)
- 8) Allowed psychiatric co-morbid conditions, such as anxiety disorders, PTSD and substance use (as long as do NOT meet abuse or dependence criteria according to the SCID-I in the past 2 months). Current Marijuana abuse is allowed during the study.

#### Exclusion criteria:

1. CANNOT be on any :

Anti-inflammatory: NSAIDs:

- Aspirin (bufferin, bayer aspirin, ecotrin),
- diflunisal (dolobid, diflunisal),

- Salsalate (amigesic, salflex),
- Ibuprofen (motrin, advil),
- Naproxen (naprosyn, aleve, midol extended relief),
- Fenoprofen (nalfon),
- Ketoprofen (actron),
- dexketoprofen (ketron D),
- Flurbiprofen (ansaid),
- Oxaprozin (daypro),
- Loxoprofen (loxfen, loxonin),
- Indomethacin (indocin, indocin SR),
- Silindac (clinoril), Etodolac (Iodine),
- Ketorolac (toradol), diclofenac (voltaren, cataflan),
- Nabumetone (Relafen)
- Piroxicam (feldene),
- Meloxicam (mobic),
- Tenoxicam (mobiflex),
- Lornoxicam (xefo),
- mefenamic acid (ponstel),
- meclofenamic acid (meclofenamate sodium),
- celecoxib (celebrex)

Anticoagulants:

- Coumadin (Warfarin), Heparin
- Anti-oxidant agents
- Fish oil
- NAC ( N-acetyl cysteine)

2. Pregnancy

3. CANNOT change the dose of the psychotropic medications during the trial

We have set our inclusion criteria to allow maximal generalizability of the results to the aggregate group of patients with BD treated in common outpatient settings, so we will allow inclusion of patients with co-morbid conditions, substance abuse, and bipolar type II. The feasibility of the proposed study is facilitated by the **University of Texas (UT) Center of Excellence on Mood Disorders**, co-directed by Drs. [name] and [name]. Our group has

an established track record of enrolling BD patients for a multitude of clinical neuroscience and clinical psychopharmacology studies.

**Study procedures:**

The study will be carried out at the outpatient clinics affiliated with the UT Health Science Center at Houston. After signing informed consent, patients will be submitted initially to a SCID-I interview to confirm the psychiatric diagnosis, followed by a physical examination and routine labs (CBC, liver function tests, electrolytes, kidney functions tests, thyroid function tests, urinalyses) to rule out relevant medical problems. Physically healthy BD patients on psychotropic medications or combinations will be enrolled and randomly assigned to receive, orally, aspirin 1000 mg qam, NAC 1000 mg bid, combination of aspirin 1000 mg qam and NAC 1000 mg bid, or placebo. The aspirin dose will be started at 1000 mg q day, and will remain the same for 8 weeks. NAC will be administered in 500 mg capsules, two capsules p.o bid and dose will remain the same for the duration of the study. Patients can be on any mood stabilizing agents or combinations, as well as on other psychotropic medications at study entry, and the doses of those medications cannot be changed during the trial. They cannot be on any anti-inflammatory or anti-oxidant agents or anticoagulant at the point they are enrolled. If patients decompensate significantly, and/or become acutely suicidal, participation on the trial will be terminated.

If patients qualify for the study initially based on SCID-I interview, physical examination, and routine labs (CBC, liver functions tests, electrolytes, kidney function tests, thyroid function tests, HIV testing, and urinalyses), but are not currently taking an approved psychotropic medication or combinations they are eligible to participate in a lead-in phase. This phase would be starting at their screening visit and last approximately 6 to 8 weeks depending on the patient's mood. During this lead-in phase, either the PI or Co-PI will evaluate the patient and prescribe either Lithium or Depakote. The patient will be monitored during this treatment phase by the PI or Co-PI and will return after two weeks for an evaluation. The evaluation will include CSSR-S and adverse effects. If the patient is prescribed lithium, their lithium levels will be tested. The patient will continue to follow up every two weeks. At the 4 week visit, the patient will also come in for evaluation (CSSR-S and adverse effects). At the 6 week visit, the patient will be re-evaluated for the double-blind study trial. If the patient has been on an adequate dose of the psychotropic medication for at least 4 weeks and score greater than 20 on the Montgomery-Asberg Depression Rating Scale (MADRS), then they will be enrolled. If they do not meet inclusion criteria at the week 6 lead-in phase visit, they will return at Week 8 and be re-evaluated. PI and Co-PI will continue to prescribe the psychotropic medication throughout the lead-in phase (up to 8 weeks) and through the trial (up to 16 weeks).

During the lead-in phase participants will not be compensated. They will receive a voucher for their parking for each visit. They will be responsible for filling and paying for all prescriptions in both the lead-in phase and through the trial (up to 16 weeks).

Upon completion of the first 8-week double-blind trial, patients who responded to the active medication will continued on the same study drug for an additional 8 week double-blind treatment. The non-responders to one of the study drugs will be re-randomized for one of the other three groups of study not received and will remain in treatment for an additional 8 week double-blind treatment. Treatment response will be defined as improvement in the **MADRS scores of at least 50%**.

During the first 8-week trial, patients will be seen at weeks 0, 1, 2, 3, 4, 6 and 8 for clinical assessment and mood ratings. During the continuation trial, they will be seen at weeks 8, 10, 12, 14 and 16. The main outcome measure for the study will be the scores on the Montgomery-Asberg Depression Rating Scale, MADRAS [62]. All patients will also be assessed with the Young Mania Rating Scale, YMRS [63], the Clinical Global Impression-Bipolar version, CGI-BP [64], and the UKU side-effects scale [65]. In all visits, patients will be seen by the study psychiatrist and the research staff will complete mood ratings with the MADRAS, YMRS, CGI-BD, and the UKU side-effects scale.

At baseline (before randomization), week 8 and week 16 blood will be sampled for proinflammatory markers (C-reactive protein, soluble interleukin (IL)-2 receptor, IL-6 and tumor necrosis factor (TNF)-alpha), and oxidative stress

markers (superoxide dismutase activity and catalase activity, serum thiobarbituric acid reactive substances (TBARS)), which have been reported to be elevated in BD patients [34] [33] [35]. These blood samples will be stored for possible future research on biomarkers or future genetic studies for up to 20 years, for use in pharmacogenetic research during this 20 year timeframe. The samples will be stored at the Wet Lab, in a double locked -80 degrees freezer, at [REDACTED]

[REDACTED] for future use studying factors of Bipolar Disorder. When (or before) the 20 year period ends, the blood sample will be destroyed.

Patients will complete neuropsychological testing at baseline and Week 16. The testing will include CANTAB, WASI, and WRAT assessments and will take approximately 3-4 hours.

At the screening visit, week 8, and week 16 we will also be testing the Lithium levels in all patients that have been prescribed and currently taking the medication for study purposes. This extra test will be conducted for the safety of the patient and more Lithium level tests can be ordered under the PI's discretion throughout the 16 week trial.

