### **Safety considerations:**

Aspirin is a safe medication for administration to humans and is approved by the FDA as an anti-inflammatory and analgesic agent. The dose proposed for this study is within the safety range as per medication package. Its side-effect profile is overall very favorable and it has met widespread use worldwide over the past decades. The main safety issues relate to the possibility of gastrointestinal complications, which are rare (and will be closely monitored in the weekly or biweekly visits that the study requires), and the propensity to interfere with coagulation and cause consequent bleeding (which will be prevented by excluding any individuals on use of anticoagulants or with active bleeding problems). There were a few case reports and small case series with other non-steroidal anti-inflammatory agents suggesting worsening of depressive symptoms related to treatment (e.g., indomethacin, ibuprofen, naproxen), but those were uncontrolled reports with individuals who suffered from other medical illnesses (rheumatologic diseases) [66] [67]. For our proposed trial, because some patients may be on lithium at the time they start on aspirin, we will exclude individuals with pre-existing cardiac and kidney disease. For patients on lithium, we will carefully monitor their serum lithium levels every two weeks during the course of the trial. Therefore, at the doses that are being proposed we do not anticipate any significant problems related to safety of the proposed intervention.

NAC is a safe compound that is commonly available and utilized over-the-counter. In a recent study [54] the tolerability was excellent and main side effects included changes in energy level, headaches, heartburn and joint pain.

Blood Draws: When the blood is drawn, there may be some minimal discomfort and/or bruising. Infection, excess bleeding, clotting, or fainting is also possible, although unlikely. All usual precautions will be taken to prevent these possibilities and these risks will be minimized by using trained staff to perform the blood draws.

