Women Able to Become Pregnant: Participation in this study may involve risks to an embryo, fetus, or unborn child. If the subject is a female and able to become pregnant, a urine pregnancy test will be performed which must be negative prior to enrolling into the study, and the subject must agree not to become pregnant during the study. Urine pregnancy tests will be performed at Screening visit and week 8. The study staff will review adequate birth control methods with the subject and will remind her that she should not become pregnant during the study. Appropriate methods of birth control include: hormonal contraceptives (such as birth control pills, patches, and implants), barrier methods (such as a condom and diaphragms and spermicidal foam or jelly, surgical (hysterectomy or tubal ligation) or intrauterine device (IUD). The subject will be instructed to notify the study doctor immediately if there is a chance that she has become pregnant.

Also, if the subject is breast-feeding an infant or plan on breast-feeding an infant, she must notify the study doctor. It is not known if this drug is excreted in human milk; therefore, breast-feeding is not permitted during the study.

**Breach of Confidentiality:** Every effort will be made to protect the subject identity and information during the study. All lab work and scan reports will be de-identified and the medical records will be protected. However, there is a small chance that the subject information may be viewed by someone that is not involved in the research study.

The study drug must be taken only by the person for whom it has been prescribed, and it must be kept out of the reach of children or persons of limited capacity to read or understand.

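### Lead-in patients can be randomised on pregnancy, kidney and liver tests about 6 to 8 weeks old, with the kidney and liver results predating their new lithium or Depakote

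*Combined protocol and SAP*

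**What the plan says.** Under Study procedures, a patient who passes the diagnostic interview, physical examination and routine laboratory tests (kidney and liver function among them), but is not on a suitable medication, may enter a lead-in on lithium or Depakote. On timing: "This phase would be starting at their screening visit and last approximately 6 to 8 weeks depending on the patient's mood".

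The lead-in visits fall at weeks 2, 4 and 6, and at week 8 if needed. Their listed content is: "The evaluation will include CSSR-S and adverse effects. If the patient is prescribed lithium, their lithium levels will be tested". At week 6 the patient is re-evaluated for the trial. The stated conditions for enrolment are an adequate dose for at least 4 weeks and a MADRS score above 20. Otherwise: "If they do not meet inclusion criteria at the week 6 lead-in phase visit, they will return at Week 8 and be re-evaluated".

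The inclusion criteria require: "No CURRENT liver, kidney, heart disease or ulcers or bleeding dyscrasia". Pregnancy is an exclusion. The Safety considerations section calls for a urine pregnancy test "which must be negative prior to enrolling into the study", and gives the schedule: "Urine pregnancy tests will be performed at Screening visit and week 8".

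Lithium monitoring is described twice. Study procedures says "At the screening visit, week 8, and week 16 we will also be testing the Lithium levels in all patients", limited to those taking lithium. Safety considerations says "For patients on lithium, we will carefully monitor their serum lithium levels every two weeks during the course of the trial". The two differ on frequency, but both concern lithium levels only.

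**The concern.** For a direct entrant, the screening tests are taken on the medication the patient will continue during the trial. For a lead-in patient they are taken before a new drug is started, and 6 to 8 weeks then pass before randomisation. Results from screening cannot show a pregnancy, or a kidney or liver problem, that arises in that time.

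The plan's own reasoning makes the timing matter. Safety considerations justifies excluding kidney and cardiac disease on the ground that some patients will be on lithium when aspirin begins. The relevant moment is therefore the start of study drug. In a lead-in patient given lithium, the only scheduled kidney result predates both drugs. A patient given Depakote has no laboratory test listed in the lead-in at all.

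At stake is patient safety. Someone the plan means to exclude could start study drug, and two of the four arms contain aspirin 1000 mg daily. A pregnancy that began in the lead-in might not be found by a scheduled test until trial week 8.

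**Working it through.** The plan gives no figure of its own to reproduce. The check sets the scheduled time points side by side and adds the intervals.

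**Inputs**

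| Item | Value | Where stated |
|---|---|---|
| Start of lead-in | Screening visit | Study procedures |
| Length of lead-in | About 6 to 8 weeks | Study procedures |
| Kidney and liver tests | At first qualification, before the lead-in drug | Study procedures |
| Tests listed at lead-in visits | Lithium level, if on lithium | Study procedures |
| Blood draw before randomisation | Inflammatory and oxidative stress markers | Study procedures |
| Pregnancy tests | Screening and week 8 | Safety considerations |
| Length of trial | 16 weeks | Study design |

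Assumption: randomisation takes place at, or shortly after, the lead-in week-6 or week-8 visit.

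**Step 1. Age of results at randomisation.** Age = length of lead-in = 6 to 8 weeks, for the pregnancy, kidney and liver tests alike.

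**Step 2. Repeats before randomisation.** Lead-in visits: weeks 2, 4, 6 = 3, or 4 with week 8. Visits listing a pregnancy, kidney or liver test: 0. The baseline blood draw lists none of these either.

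**Step 3. Interval between scheduled pregnancy tests.** Lead-in + 8 weeks on study drug = 6 + 8 = 14 weeks to 8 + 8 = 16 weeks. For a direct entrant it is 8 weeks plus a screening-to-baseline gap that the document does not give.

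**Step 4. Period covered by one listed kidney and liver result.** The week-8 and week-16 blood tests list no kidney or liver function. So the period is 6 + 16 = 22 weeks to 8 + 16 = 24 weeks.

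**Step 5. Other reading of week 8.** In the pregnancy-test schedule, week 8 most naturally means trial week 8. If it meant lead-in week 8, a woman enrolled at lead-in week 6 would still have no repeat test before randomisation, and a direct entrant would have no second test at all.

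**Step 6. After the fix.** With repeats at the enrolment visit, results are about 0 weeks old at randomisation instead of 6 to 8. The interval from the last test before randomisation to the week-8 pregnancy test falls from 14 to 16 weeks to about 8.

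**The case against.** The strongest reply is that this reads silence as absence. The protocol is a narrative with no schedule table. Lead-in patients qualify only provisionally, are followed by a physician, and are re-evaluated against the inclusion criteria, one of which concerns current kidney and liver disease. A physician applying that criterion after starting lithium or Depakote may well order tests, and nothing forbids it. The pregnancy rule is tied to enrolment, which for these patients comes after the lead-in. There are also partial safeguards: lithium levels, adverse-effect checks, contraception counselling and the duty to report a possible pregnancy.

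Part of this stands. The text supports the statement that repeat tests are not scheduled, not that they would never be done. The exclusions still formally apply, and the safeguards reduce the consequence. Of the 14 to 16 weeks between pregnancy tests, 8 are the ordinary on-trial interval that direct entrants share. Of the 22 to 24 weeks, 16 are on-trial weeks that concern every participant and are not cured by a test at enrolment. A direct entrant who conceives after screening would also go undetected by a scheduled test until week 8, so the lead-in differs in degree.

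The point survives all the same. Discretion is not a scheduled test. The pregnancy rule sets no maximum age, so a negative result 6 to 8 weeks old satisfies it. The stated enrolment rule turns on dose and MADRS and says nothing about laboratory results. Lithium levels are not kidney or liver tests and do not apply to patients on Depakote. Counselling and self-report cannot find a pregnancy the patient does not know about.

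**Conclusion.** The concern holds. Followed as written, the plan allows a lead-in patient to be randomised on pregnancy, kidney and liver results about 6 to 8 weeks old, and the kidney and liver results predate the newly started drug. This rests on randomisation following the week-6 or week-8 lead-in visit and on reading week 8 of the pregnancy schedule as trial week 8. The second assumption affects only part of the finding, since women enrolled at lead-in week 6 are exposed on either reading.

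The document gives neither the size of the lead-in group nor the chance of a pregnancy or organ change in it, so the actual risk cannot be estimated. The concern about aspirin with lithium is limited to lead-in patients given lithium who are assigned to an aspirin-containing arm. This is a safety gap in the assessment schedule that should be closed. It has no claimed effect on power, type I error or the comparison between arms.

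**What to change.** At the lead-in visit where the patient is enrolled (week 6 or week 8), repeat the urine pregnancy test in women able to become pregnant and the screening kidney and liver tests in all lead-in patients. Require the results before randomisation. State this in the lead-in paragraph of Study procedures, and add the time point to the pregnancy-test schedule in Safety considerations. This sets no new clinical threshold; it checks the existing criteria at the moment study drug starts.

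The cost is one urine test where applicable and one routine panel per lead-in patient, at a visit that already exists. There may be a short wait for results or an extra visit, a few more exclusions, and a small protocol amendment.
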